6.5. Extent of Exposure

Extent of exposure to Belantamab Mafodotin will be summarized.

The number of cycles administered to study treatment will be summarised with mean, median, standard deviation, minimum, and maximum. The number and percentage of participants who received a given number of cycles (<4, 4, and >4 cycles) will be reported. The duration of exposure to study treatment in days (from first day to last day of treatment) will be calculated and summarized using mean, median, standard deviation, minimum, and maximum. A horizontal bar graph of duration of treatment will be produced that displays duration of treatment in months for each participant.

A by participant summary listing of data on exposure to all study treatments will be produced.

Dose reductions will be summarised by number of reductions and reasons for reductions. Dose delays will be summarised by number of delays, reasons for the delays, and delay duration (days). The number and percentage of the delays for intervals of 1-21, 22-42 and >42 days will be computed.

Duration of delays is defined as period from the expected start date of dose to actual start date of current dose. Calculation: (actual start date of current dose - expected start date of dose). Expected start date of dose = actual start date of previous dose + 21.

The summaries of dose modifications will be provided. All the dose reductions and dose delays will be listed.

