- 34. Belantamab mafodotin administration: Study drug administration ± 3 -day window.
- 35. Corneal management information:
 - a. Prophylactic preservative-free artificial tears must be administered in each eye at least 4-8 times daily beginning on Cycle 1 Day 1 until end of treatment.
 - b. At the start of each infusion, participants may apply cooling eye masks to their eyes for approximately 1 hour or as long as tolerated.
- 36. All related SAEs are to be collected from consent through PD follow-up.
- 37. Additional assessments may be conducted for those participants who experience a worsening in visual function. Participants who discontinue participation in the study will continue to be assessed during follow-up until resolution of visual symptoms. Continue to follow up with participants via telephone who are still experiencing visual symptoms even after discontinuation.

TMF-14065056 208465

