6.6. Dose Modification

Table 4 details the permitted dose modifications of belantamab mafodotin. Table 5 and Table 6 contain dose modification guidance for drug-related AEs. See Table 7 for dose modification guidelines for belantamab mafodotin treatment-related changes in vision.

Table 4 Permitted Dose Reductions

Starting dose	Dose reduction
2.5 mg/kg	1.9 mg/kg
3.4 mg/kg	2.5 mg/kg, 1.9 mg/kg

If the participant cannot tolerate the drug after the allowed dose reduction of belantamab mafodotin to the lowest allowed dose of 1.9 mg/kg, he or she must discontinue treatment for lack of tolerability.

In case of full resolution of symptoms which lead to dose reduction, further treatment at the previous dose level may be considered by the investigator.

If a dose is delayed, the participant should wait for the next scheduled dose to resume treatment. In individual cases where in the judgment of the Investigator waiting a full cycle to resume treatment after delay (skipping dose) related to toxicity which has resolved would be detrimental to the participant's health, the PI should contact the Medical Monitor to discuss an earlier re-start. An earlier re-start may be considered only for participants who have recovered from toxicity to at least ≤Grade 1. The dosing with belantamab mafodotin cannot occur more frequently than every 21 days (±3-day

window). In such cases, efficacy and safety assessments must remain every 3 weeks in line with initial efficacy and safety assessments on study, which may result in 2 separate visits (1 for dosing, 1 for disease assessments). Evaluations associated with a dose would be entered into the eCRF under the next scheduled cycle.

Resuming treatment with belantamab mafodotin will be possible with or without dose reduction after the toxicity has resolved to Grade 1 or less.

Table 5 Dose Modification Guidelines for Belantamab Mafodotin-Related Adverse Events

Toxicity	Grade/description of toxicity	Recommendations for Belantamab Mafodotin
Elevated serum creatinine which cannot be explained by concomitant sepsis, TLS, other severe condition with fever, or dehydration	If absolute serum creatinine increases from baseline by >0.5 mg/dL	 Repeat serum creatinine within 48 hours If confirmed: withhold therapy, institute treatment and monitoring as clinically indicated, and follow for resolution Discuss any further dosing with Medical Monitora

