10.3.1.2. Pharmacokinetic Parameters

To assess the extent of accumulation following belantamab mafodotin repeat dosing, the observed accumulation ratio (Ro) for belantamab mafodotin, total antibody, and cys-mcMMAF will be determined as ratio of CEOI and Ctrough at Cycle 4 to CEOI and Ctrough at Cycle 1, respectively, using the data collected under Protocol 208465/Amendment 3.

Previous studies indicate that the pharmacokinetics for the third consecutive dose given at the planned interval will be at steady state. Therefore, based on the planned sampling scheme, accumulation ratios will be derived using the CEOI at Cycle 4 for Ro(CEOI) and Ctrough at Cycle 3 (predose at C4D1) for Ro(Ctrough). Participants must receive the same dose without delay or change for the first three cycles to derive Ro(Ctrough) and for the first four cycles to derive Ro(CEOI) (i.e., with dosing delays of ≤ 3 days).

$Ro(CEOI) = CEOI \text{ at C4D1} / CEOI \text{ at C1D1};$

$Ro(Ctrough) = \text{Cycle 3 trough} / \text{Cycle 1 trough}$

Accumulation ratios of CEOI and Ctrough, and other Pharmacokinetic Parameters in [Table 2](#) will be summarised using descriptive statistics for belantamab mafodotin (ADC, total antibody and cys-mcMMAF) by planned initial dose level, graphically presented (where appropriate) and listed.

CCI

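### SAP 6.5 measures dose delays with no tolerance, so doses given 1 to 3 days late, inside the protocol's dosing window, can be reported as delays

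*SAP*

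**What the plan says.** SAP 6.5 (Extent of Exposure) sets the reference date as "Expected start date of dose = actual start date of previous dose + 21". It takes the delay duration as the plain difference: "Calculation: (actual start date of current dose - expected start date of dose"). No tolerance is subtracted. The categories follow: "The number and percentage of the delays for intervals of 1-21, 22-42 and >42 days will be computed". The section also asks for the number of delays and the reasons for them, and for all delays to be listed. SAP 6.4 uses the number of dose delays as one of the measures that characterise compliance.

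Three other places bear on the same interval:

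- Footnote 34 to the Protocol's Schedule of Activities reads "Study drug administration ± 3 -day window". SAP Appendix 2 repeats this footnote.
- Protocol 6.6 sets a minimum interval of 21 days between doses, with the same 3-day window. It also says "If a dose is delayed, the participant should wait for the next scheduled dose to resume treatment", and then allows an earlier restart in individual cases after discussion with the Medical Monitor.
- For the accumulation ratios, SAP 10.3.1.2 states "Participants must receive the same dose without delay or change for the first three cycles" (four cycles for the end-of-infusion ratio). It explains this condition as dosing delays of no more than 3 days.

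**The concern.** A dose given 23 days after the previous one is inside the protocol's dosing window and meets the pharmacokinetic condition of dosing without delay. Under the SAP 6.5 formula it has a delay of 2 days and falls in the 1-21 day category. One SAP can therefore give the same dose two different statuses.

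What is at stake is how the exposure and compliance displays read. A participant dosed entirely within the window could appear as having delayed doses. The 1-21 day category would combine one-day scheduling shifts with holds of a whole cycle. The table of reasons would either gain scheduling entries or contain delays with no reason. Cohorts have up to 6 evaluable participants (Protocol 4.1 and 9.2), so one participant counted this way moves a percentage by 1/6, or about 17 points.

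**Working it through.** The plan states no delay count, so there is no figure to reproduce. The check applies its rule to possible dosing gaps.

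**Inputs.** Expected date = previous actual dose + 21 days; delay = actual − expected; categories 1-21, 22-42 and >42 days (SAP 6.5). Dosing window of 3 days (Protocol Schedule of Activities footnote 34; Protocol 6.6). Delays of up to 3 days accepted (SAP 10.3.1.2).

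**Step 1: the rule by gap since the last dose.**

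| Gap (days) | Actual − expected | SAP 6.5 category | Accepted as without delay in SAP 10.3.1.2 | Category if a delay must exceed 3 days |
|---|---|---|---|---|
| 21 | 0 | none | yes | none |
| 22 | 1 | 1-21 | yes | none |
| 23 | 2 | 1-21 | yes | none |
| 24 | 3 | 1-21 | yes | none |
| 25 | 4 | 1-21 | no | 4-21 |
| 42 | 21 | 1-21 | no | 4-21 |
| 43 | 22 | 22-42 | no | 22-42 |

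The two SAP sections differ on exactly three gaps: 22, 23 and 24 days. Omitting the tolerance can add delays but cannot remove any, so the effect runs one way.

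**Step 2: scale.** Let p be the share of doses after the first that are given 1 to 3 days late. The documents do not give p; 5%, 10% and 20% are assumptions. With k doses after the first, treated as independent, the chance that a participant shows at least one such delay is 1 − (1 − p)^k. For k = 3, which reaches Cycle 4:

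- p = 5%: 1 − 0.95³ = 14%
- p = 10%: 1 − 0.90³ = 27%
- p = 20%: 1 − 0.80³ = 49%

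Six participants with three later doses each have 18 such doses, so the expected number of added delays is 18p: 0.9, 1.8 and 3.6. The chance grows with time on treatment. For k = 10 it is 40%, 65% and 89%.

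**Step 3: does a 3-day tolerance remove the problem?** It does if the window is counted from the previous dose. If visits follow a fixed calendar, a dose 3 days early followed by one 3 days late gives a gap of 27 days and a computed delay of 6 days, with both doses in window. If each dose fell with equal chance on any of the 7 window days, 6 of the 49 pairs (12%) would give a computed delay above 3 days. The tolerance therefore removes most such cases but not all.

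**The case against.** The strongest reply is that SAP 6.5 defines how long a delay lasts, not what creates a delay record. The section summarises delays with their reasons, which fits delays recorded by the site at least as well as delays derived from dates. If only recorded delays enter, few in-window shifts would be counted. This stands, and it is why the conclusion is conditional. The SAP does not say which source it uses, and a lower bound of 1 day admits the short shifts.

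A second reply is that SAP 10.3.1.2 selects participants for a steady-state calculation and itself calls shifts of up to 3 days delays, so it is not a general definition. That is fair. It lessens the contradiction within the SAP but leaves the mismatch with the protocol window.

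Third, every delay is listed with its duration, and the study is small enough for a reader to separate the short shifts by hand. This also stands, and it limits the harm.

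Two stronger readings are tempting. A reader might set Table 1.140 beside the 51% and 67% in Protocol 2.3.2 and infer that this trial would overstate intolerance against the earlier studies. Those percentages concern adverse events leading to dose delays. This trial reports that measure separately (SAP 8.2 and 8.5), and the SAP does not tie it to the date formula. The documents also do not say how the earlier studies defined a delay. A reader might also infer that any delay shorter than a cycle is only a scheduling shift, because participants normally wait for the next scheduled dose. The early-restart provision in Protocol 6.6 rules that out, so some short holds may be due to toxicity.

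**Conclusion.** The point holds in a limited form. Applied as written to dosing dates, SAP 6.5 places doses given 22 to 24 days after the last one in the delay table, although the protocol window covers them and SAP 10.3.1.2 accepts them. This can inflate the delay count and blur its meaning in Table 1.140 and Listing 1.100, and probably in Table 1.150.

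The amount cannot be found from the documents. The range of 14% to 49% of participants rests wholly on assumed lateness of 5% to 20%, three later doses, independence between doses, and delays being derived from dates.

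DLT, adverse event (including delays caused by adverse events) and response analyses do not use the formula, and no hypothesis is tested. Severity is minor and confidence moderate.

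**What to change.** In SAP 6.5:

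1. State whether delays are derived from dosing dates or taken from the eCRF.
2. Count a date-derived delay only when actual minus expected exceeds 3 days, so that the first category becomes 4-21 days.
3. Show shifts of 1 to 3 days on a separate within-window line. Leave them out of the delay count unless the site recorded a toxicity reason, so that short toxicity holds are kept.
4. Use the same wording in SAP 10.3.1.2.

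This changes an analysis definition only and no dosing rule. The cost is a few lines of SAP text and small programming changes. The remaining weakness is the fixed-calendar case, in which an early dose followed by a late one can still show as a delay of more than 3 days with both in window. A footnote to Table 1.140 can say so.

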6.6. Concomitant Medications

Concomitant medications will be coded using GSK Drug coding dictionary, summarized, and listed. The summary of concomitant medications will show the number and percentage of participants taking concomitant medications by Ingredient. Multi-ingredient products will be summarized by their separate ingredients rather than as a combination of ingredients. Anatomical Therapeutic Chemical (ATC) classification Level 1 (Body

System) information will be included in the dataset created but will not appear on the listing or summary.

In the summary of concomitant medications, each participant is counted once within each unique ingredient. For example, if a participant takes Amoxycillin on two separate occasions, the participant is counted only once under the ingredient “Amoxycillin”. In the summary of concomitant medications, the ingredients will be summarized by the base only, using CMBASECD and CMBASE. Note: In order to be considered a concomitant medication, the concomitant medication must have been taken at some point during the on-treatment window.

Blood products or blood supportive care products with onset date within the on-therapy window will be included in the summary tables. The frequency and percentage of subjects using blood products and blood supportive care products after the start of study medication will be provided. Supporting listings will also be provided.

7. EFFICACY ANALYSES

The efficacy analyses will be based on the All Treated population, unless otherwise specified.

Details of the planned displays are provided in [Appendix 12: List of Data Displays](#) and will be based on GSK data standards and statistical principles.

Unless otherwise specified, the following endpoints / variables will be summarised using descriptive statistics, graphically presented (where appropriate) and listed.

7.1. Objective response rate (ORR)

ORR is defined as the percentage of participants with a confirmed partial response (PR) or better (i.e., VGPR, CR and stringent complete response [sCR]) as assessed according to IMWG Uniform Response Criteria for Multiple Myeloma 2016 (See Protocol Appendix 6) by the Investigator.

ORR and the associated 2-sided 95% exact confidence intervals will be provided. A list of investigator-assessed response at each visit will be listed.

The following rule of confirmation will be used to confirm the response (i.e., PR, VGPR, CR and sCR):

- PR: two consecutive response of PR or better at any time before starting any new therapy.
- VGPR: two consecutive responses of VGPR or better at any time before starting any new therapy.
- CR: two consecutive response of CR or better (i.e. sCR) at any time before starting any new therapy.
- sCR: two consecutive responses of sCR at any time before starting any new therapy.

7.1.1. Derivation of Confirmed Response

The derivation of confirmed response shall be based on the algorithm specified in [Table 1](#). The date of the first of the two consecutive assessments will be used as the date of the confirmed response.

Table 1 Response confirmation algorithm

#	Response at the First Time Point	Response at Subsequent Disease Assessment ¹	Confirmed Response at the First Time Point
1	sCR	sCR	sCR
2	sCR	CR	CR
3	CR	sCR/CR	
4	sCR/CR	VGPR	VGPR
5	VGPR	sCR/CR/VGPR	
6	sCR/CR/VGPR	PR	PR
7	PR	sCR/CR/VGPR/PR	

#	Response at the First Time Point	Response at Subsequent Disease Assessment ¹	Confirmed Response at the First Time Point
8	sCR/CR/VGPR/PR	MR	MR
9	MR	sCR/CR/VGPR/PR/MR	
10	sCR/CR/VGPR/PR/MR	SD	SD
11	sCR/CR/VGPR/PR/MR	PD (any reason) OR No subsequent disease assessment: subject died or discontinued study or started new anti-cancer therapy before further adequate disease assessment	NE
12	PD (due to reasons other than imaging, i.e., plasmacytoma or bone lesion)	PD (any reason) including PD after initiation of new anti-cancer therapy OR No subsequent disease assessment: subject died due to PD before further adequate disease assessment (including death due to PD after initiation of new anti-cancer therapy)	PD
13	PD (due to reasons other than imaging, i.e., plasmacytoma or bone lesion)	sCR/CR/VGPR/PR/MR/SD OR No subsequent disease assessment: subject died due to reasons other than PD before further adequate disease assessment OR No subsequent disease assessment: subject discontinued study before further adequate disease assessment	NE
14	sCR/CR/VGPR/PR/MR/PD (due to reasons other than imaging, i.e., plasmacytoma or bone lesion)	No subsequent disease assessment: subject has not died, discontinued from study or (except for PD) started new anti-cancer therapy; but as yet has no further adequate disease assessments	Unconfirmed sCR/CR/VGPR/PR/MR/PD. Will be categorized as NE for final ORR analysis. For ORR analysis in IA, the UC response (PR or better) will be counted as responder.
15	SD	Any	SD

#	Response at the First Time Point	Response at Subsequent Disease Assessment ¹	Confirmed Response at the First Time Point
		OR No subsequent disease assessment	
16	PD due to imaging (plasmacytoma or bone lesion)	Any OR No subsequent disease assessment	PD
17	NE or missing	Any OR No subsequent disease assessment	NE

[figure not shown]
1. Subsequent disease assessment is defined as the next adequate (not missing or NE) disease assessment following the first timepoint before (or on the same date of) start of new anti-cancer therapy except for confirmation of PD, for which PD or death due to PD after new anti-cancer therapy are considered for confirmation of PD. No minimal time interval is required for the subsequent disease assessment, but a different sample is required for confirmation.
2. PD due to imaging (i.e., plasmacytoma or bone lesion) does not need to be confirmed.
3. Where criteria are not mutually exclusive, take the first that applies.

7.2. Duration of response (DOR)

DOR is defined as the duration from the time documented evidence of confirmed PR or better is first met until the first date that progressive disease or death due to PD, whichever occurs first, among participants who achieve a response (i.e. confirmed PR or better).

DOR will be summarized using Kaplan-Meier curves if applicable. If there are a sufficient number of progressions or death due to PD among the responders, median DOR, first and third quartiles and 95% CI, will be estimated using the Brookmeyer-Crowley method [Brookmeyer, 1982]. A listing of DOR time will also be provided.

CCI

8. SAFETY ANALYSES

The primary endpoints are adverse events, i.e., the number (%) of participants with DLTs, and the number (%) of participants with AEs.

The DLT analyses will be based on the DLT Evaluable population, unless otherwise specified.

The safety analyses (except the DLT analysis) will be based on the All Treated population, unless otherwise specified.

8.1. Dose Limiting Toxicity Analyses

The DLTs is one of the primary endpoints, the number and proportion of participants in the DLT population who experienced DLT during the Cycle 1 of study treatment will be presented. Details of the planned displays are presented in [Appendix 12: List of Data Displays](#).

8.2. Adverse Events Analyses

Adverse events analyses including the analysis of adverse events (AEs), serious adverse events (SAEs) and other significant AEs will be based on GSK Core Data Standards. The details of the planned displays are provided in [Appendix 12: List of Data Displays](#).

An overview summary of AEs, including counts and percentages of participants with any AE, AEs related to study treatment, Grade 3 or 4 AEs, Grade 3 or 4 AEs related to study treatment, AEs leading to permanent discontinuation of study treatment, AE leading to dose reductions, AEs leading to dose delays OR interruptions, SAEs, SAEs related to study treatment, fatal SAEs, and fatal SAEs related to study treatment will be produced.

A summary of non-serious AEs will be provided. The summary will be displayed by PT.

The relationship between PT and Verbatim Text will be displayed.

Adverse events (AEs) will be coded using the standard Medical Dictionary for Regulatory Activities (MedDRA). Severity of corneal events will be graded using the scale provided in Table 7 of the Study Protocol. The severity of other AEs will be graded by the investigator according to the National Cancer Institute-Common Toxicity Criteria for Adverse Events (NCI-CTCAE) (version 5.0).

A summary of number and percentage of participants with any adverse events by maximum grade will be produced. AEs will be sorted by Preferred term (PT) in descending order of total incidence. The summary will use the following algorithms for counting the participant:

- **Preferred term row:** Participants experiencing the same AE preferred term several times with different grades will only be counted once with the maximum grade.

- **Any event row:** Each participant with at least one adverse event will be counted only once at the maximum grade no matter how many events they have.

In addition, the frequency and percentage of AEs (all grades) will be summarized and displayed in descending order of total incidence by PT only.

A separate summary will be provided for study treatment-related AEs. A study treatment-related AE is defined as an AE for which the investigator classifies the relationship to study treatment as “Yes”. A worst-case scenario approach will be taken to handle missing relatedness data, i.e. the summary table will include events with the relationship to study treatment as ‘Yes’ or missing. The summary table will be displayed by maximum grade sorted by PT in descending order of total incidence.

In addition, AEs of maximum grade of 3 or higher will be summarized separately by PT.

All AEs will be listed. Additionally, a listing of participant IDs for each individual AE will be produced.

The details of the planned displays are provided in [Appendix 12: List of Data Displays](#).

8.3. Adverse Events of Special Interest Analyses

Adverse events of special interest (AESI) for belantamab mafodotin are corneal events, thrombocytopenia and infusion related reactions.

Summaries of the number and percentage of participants with these events will be provided for each type of events separately by preferred term and maximum grade. The time of onset and duration of first occurrence of corneal events will be summarized using summary statistics mean, standard deviation, median, minimum value, and maximum. The number and percentage of participants who have time of onset of first occurrence (1-21, 22-42, 43-63, >63 days) will be reported. The number and percentage of participants who have duration of first occurrence (1-21, 22-42, >42 days) will be reported.

The summary of event characteristics of corneal events and thrombocytopenia will also be provided, including number of participants with any event, number of events, number of participants with any event that is serious, number of participants with any event that is related to study treatment, number of occurrences (One, Two, Three or more), maximum grade and the action taken for the event. The percentage will be calculated in two ways, one with number of participants with event as the denominator and the other with total number of participants as the denominator. The worst-case approach will be applied at participant level for the maximum grade, i.e. a participant will only be counted once as the worst case from all the events experienced by the participant. For action taken to an event, participant will be counted once under each action, e.g. if a participant has an event leading to both study treatment discontinuation and dose reduction, the participant will be counted once under both actions.

A comprehensive list of MedDRA terms based on clinical review will be used to identify each type of event. The details of the planned displays are provided in [Appendix 12: List of Data Displays](#).

